4. STUDY DESIGN

4.1. Overall Design

This is a Phase 2b, multi-center, randomized, partial-blind [Sponsor and Participant blinded], study to assess efficacy and safety of treatment with GSK3228836 in two populations of patients with CHB (1) participants on stable nucleos(t)ide treatment and (2) participants not currently on nucleos(t)ide therapy.

Both populations of patients with CHB will be randomized into one of 4 parallel arms:

- 300 mg GSK3228836 once/week for 24 weeks (plus loading dose of 300 mg GSK3228836 on Day 4 and Day 11);
- 300 mg GSK3228836 once/week for 12 weeks (plus loading dose of 300 mg GSK3228836 on Day 4 and Day 11) followed by step-down in dose of 150 mg (plus placebo to match to maintain participant blinding) GSK3228836 once/week for 12 weeks;
- 300 mg GSK3228836 once/week for 12 weeks (plus loading dose of 300 mg GSK3228836 on Day 4 and Day 11) followed by placebo once/week for 12 weeks;
- Placebo once/week for 12 weeks followed by 300 mg GSK3228836 once/week for 12 weeks (plus placebo loading doses to match on Day 4 and Day 11, no loading dose for GSK3228836 treatment)

After the 24 weeks of dosing with GSK3228836 or placebo, there will be a post-treatment follow-up period of 24 weeks.

Populations will be stratified based on HBsAg level (HBsAg \leq 3 log IU/mL and \geq 3 log IU/mL) and whether participants are HBeAg positive or negative.

The study is a partially blinded study where participants will be blinded to the study treatment. The investigators, site staffs and pharmacist will be unblinded. GSK and contract research organization (CRO) team members will be blinded to participants' study treatment and any potentially unblinding information, unless specified otherwise in the study blinding management plan (e.g., unblinded site monitors).

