Clinical data from ISIS 505358-CS3 suggest that co-administration of GSK3228836 is unlikely to impact efficacy and safety profiles. Given the long plasma and tissue half-life of GSK3228836 (approximately 3 weeks), there is a period of at least several weeks during which there was a substantial presence of both drugs in the plasma, liver and other tissues. Potent reduction of HBV DNA was observed following initiation of tenofovir in all participants. There were no obvious differences in tenofovir potency and efficacy in participants who received 150 mg of GSK3228836 (Cohort 1), 300 mg of GSK3228836 (Cohorts 2 and 3), and placebo (no GSK3228836). There were no adverse event or clinical laboratory results that may indicate a change in tenofovir safety profile due to drug-drug interaction with GSK3228836.

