8.4. Treatment of Overdose

For this study, any dose of GSK3228836 greater than 300 mg within a 24-hour time period will be considered an overdose.

GSK does not recommend specific treatment for an overdose.

In the event of an overdose, the investigator should:

- 1. Contact the Medical Monitor immediately.
- 2. Closely monitor the participant for AE/SAE and laboratory abnormalities until GSK3228836 can no longer be detected systemically (at least 105 days).
- 3. Obtain a plasma sample for PK analysis within 1 day from the date of the last dose of study intervention if requested by the Medical Monitor (determined on a case-by-case basis).
- 4. Document the quantity of the excess dose as well as the duration of the overdosing in the CRF.

Decisions regarding dose interruptions or modifications will be made by the investigator in consultation with the Medical Monitor based on the clinical evaluation of the participant.

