8.5. Pharmacokinetics

Blood samples will be collected for measurement of plasma concentrations of GSK3228836 and/or nucleos(t)ide as specified in the SoA.

- For standard PK sampling, one pre-dose PK sample at each visit during the treatment period (except for Day 4 and Day 11) and one PK sample at any time at each visit during the off-treatment period will be collected in participants from all 8 study arms.
- For intensive PK sampling, a maximum of 13 samples in addition to the standard PK sampling may be collected from 39 participants who were on stable NA therapy at baseline (13 in each region of Japan, China, and non-Asian country/ies) at one additional time point during the study. The intensive PK sampling will be collected at one visit between Week 14 (inclusive) and Week 24 (inclusive), chosen between the site and participant. See Table 8 for sample collection timings. The timing of

sampling may be altered during the course of the study based on newly available data (e.g., to obtain data closer to the time of peak plasma concentrations) to ensure appropriate monitoring.

- At the visit for intensive PK sampling, GSK3228836 and nucleos(t)ide will be administered as close together as possible, and the date and time (24-hour clock time) of administration of both drugs will be recorded. Instructions for drug administration at the visit for intensive PK sampling will be provided by the sponsor. See SRM for details.
- Instructions for the collection and handling of biological samples will be provided by the sponsor. The actual date and time (24-hour clock time) of each sample will be recorded.
- Standard PK samples will be used to evaluate the PK of GSK3228836, and explore PK-PD relationships.
- For participants in the intensive PK sampling, samples will be used to evaluate the PK of GSK3228836 and nucleos(t)ide therapy. See Table 8.
- Samples collected for PK analyses may also be used to evaluate safety or efficacy aspects related to concerns arising during or after the study.
- Genetic analyses will not be performed on these plasma samples unless consent for this was included in the informed consent. Participant confidentiality will be maintained. At visits during which plasma samples for the determination of multiple aspects of GSK3228836 will be taken, one sample of sufficient volume can be used.

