4.3.3.2. Derived Pharmacokinetic Parameters

Pharmacokinetic parameters will be calculated by standard non-compartmental analysis using the currently supported version of WinNonlin. All calculations of non-compartmental parameters will be based on actual sampling times. Pharmacokinetic

parameters listed will be determined from the plasma concentration-time data, as data permits.

Table 6 Pharmacokinetic Parameters and Parameter Description

Parameter	Data	Analyte	Parameter Description
AUC(0-24)	Intensive PK	GSK3228836 Nucleos(t)ide	Area under the concentration-time curve from time zero up to 24 hours post-dose.
AUC(0-168)	Intensive PK	GSK3228836	Area under the concentration-time curve from time zero up to 168 hours post-dose.
Сτ	Intensive PK	Nucleos(t)ide	Concentration at the end of the dosing interval
Сτ	Sparse PK – All Subjects	GSK3228836	Concentration at the end of the dosing interval
Cmax	Intensive PK	GSK3228836 Nucleos(t)ide	Maximum observed concentration
tmax	Intensive PK	GSK3228836 Nucleos(t)ide	Time of maximum observed concentration
t½	Sparse PK – All Subjects	GSK3228836	Terminal half-life determined using concentrations collected during the off-treatment period

Sparse PK is collected weekly during the dosing period and at certain pre-specified visits during the off-treatment period. Intensive PK is collected at one visit between Week 14 (inclusive) and week 24 (inclusive).

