4.3.3.4. Statistical Analyses / Methods

Unless otherwise specified, endpoints / variables defined in Table 6 will be summarised using descriptive statistics, graphically presented (where appropriate) and listed. Descriptive statistics for continuous variables will summarise n, arithmetic mean, SD, 95% CI, median, minimum, maximum, geometric mean with associated 95% CI, and the between-participant CV (%CVb) for the geometric mean. For sparse PK summary of $C\tau$ and t1/2, additionally present 5th and 95th percentile.

Sparse PK parameters ($C\tau$ and t1/2) of GSK3228836 will be summarised and listed by treatment arm, study visit (only applies to $C\tau$), geographic region (All participants, China, Japan and East Asia). Sparse $C\tau$ -time plots will be created and compared by the same factors.

Intensive PK parameters (AUC(0-24), AUC(0-168), Cmax and tmax) of GSK3228836 will be summarised and listed by dose level (150mg and 300mg). Intensive concentration-time plots will be created and compared by the same factors.

Intensive PK parameters (AUC(0-24), $C\tau$, Cmax and tmax) of nucleos(t)ide will be summarised and listed separately for tenofovir (separately for tenofovir disoproxil fumarate and tenofovir alafenamide) and entecavir. Intensive concentration-time plots will be created separately for tenofovir (separately for tenofovir disoproxil fumarate and tenofovir alafenamide) and entecavir.

Refer to Section 4.6 for more information on geographic region subpopulations.

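### Intensive GSK3228836 PK is grouped by dose level only, which mixes dosing histories not at steady state and can bias AUC(0-168) as a description of each dose

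*Protocol*

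**What the plan says.** SAP 4.3.3.4 states that the intensive parameters AUC(0-24), AUC(0-168), Cmax and tmax "of GSK3228836 will be summarised and listed by dose level (150mg and 300mg". The concentration-time plots are to be compared on the same factor. Neither arm nor visit week is named. In the same section the sparse parameters (trough and half-life) "of GSK3228836 will be summarised and listed by treatment arm, study visit" (visit for the trough only) and region.

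The timing comes from Protocol 8.5: "The intensive PK sampling will be collected at one visit between Week 14 (inclusive) and Week 24 (inclusive), chosen between the site and participant". The profiles "may be collected from 39 participants who were on stable NA therapy at baseline", 13 in each of three regions, and no allocation by arm is given.

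Protocol 4.1 sets the dosing histories. Arm 1 takes 300 mg weekly throughout, with loading doses on Days 4 and 11. Arm 2 does the same for 12 weeks and then takes 150 mg weekly. Arm 3 is on placebo after Week 12. Arm 4 is "Placebo once/week for 12 weeks followed by 300 mg GSK3228836 once/week for 12 weeks", with no loading of active drug.

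Protocol 4.3 gives the half-life: "Given the long plasma and tissue half-life of GSK3228836 (approximately 3 weeks". SAP 4.3.3.2 defines the main exposure measure as "Area under the concentration-time curve from time zero up to 168 hours post-dose", with no steady-state label.

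**The concern.** A dose-level summary describes the dose only if the profiles in it share a comparable dosing history. Here they do not. With a half-life of about 3 weeks, an unloaded start or a halved dose at Week 13 takes several weeks to settle, and the sampling window opens at Week 14.

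At 300 mg, Arm 1 (loaded, at least 14 weeks of dosing) is combined with Arm 4 (2 to 12 weekly doses). At 150 mg the group is Arm 2, measured 2 to 12 weeks into step-down dosing. Any participant taken off hold at 150 mg under Protocol Table 6 would also fall in that group, with yet another history.

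The direction is predictable: 300 mg exposure reads low and 150 mg exposure reads high. A reader comparing the two AUC(0-168) rows could take this for less-than-proportional kinetics. The objective affected is the secondary one of characterising GSK3228836 PK. No efficacy or safety endpoint is involved.

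**Working it through.** **Check on the half-life.** Protocol 8.4 asks for overdose monitoring "until GSK3228836 can no longer be detected systemically (at least 105 days". Five half-lives of 21 days is 5 × 21 = 105 days, leaving 2^-5 = 3.1%. The two figures agree. The five-half-life rule is an inference, because the protocol does not show how it reached 105. The documents give no accumulation or steady-state figure.

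**Model.** Linear superposition of the planned doses with a 21-day half-life. Let m be weeks after Week 12, so m = 2 at Week 14 and m = 12 at Week 24. Let s be the share of single-dose plasma AUC in the slow phase. The documents do not give s. Setting s = 1 (one compartment) is the upper bound at this half-life. AUC(0-168) relative to steady state for the dose being taken is:

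- Arm 4: 1 − s·2^(−m/3).
- Arm 1: without loading, Week 12 would be at 1 − 2^(−12/3) = 93.75%. The Day 4 and Day 11 doses add about 4.05 points, giving 97.8%. After that it is 1 − 0.022·s·2^(−m/3).
- Arm 2: the 300 mg residue counts double against a 150 mg reference, so 1 + (2 × 0.978 − 1)·s·2^(−m/3) = 1 + 0.956·s·2^(−m/3).

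**By week, s = 1**

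| Week | Arm 1 | Arm 2 | Arm 4 |
|---|---|---|---|
| 14 | 98.6% | 160% | 37% |
| 16 | 99.1% | 138% | 60% |
| 18 | 99.5% | 124% | 75% |
| 20 | 99.7% | 115% | 84% |
| 24 | 99.9% | 106% | 94% |

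**Average over Weeks 14 to 24.** This assumes an even spread of visits, which the documents do not state. The mean of 2^(−m/3) for m = 2 to 12 is 0.256. Arm 1 is 0.994, Arm 2 is 1 + 0.956 × 0.256 = 1.24, and Arm 4 is 1 − 0.256 = 0.744.

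**Expected mix.** If the 39 profiles follow the 3:3:3:1 ratio, they split 11.7 / 11.7 / 11.7 / 3.9. Arm 4 is then 3.9 / 15.6 = 25% of the 300 mg group. The Arm 3 profiles fall in placebo weeks and belong to neither dose level.

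**Effect on the summaries, s = 1**

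- Pooled 300 mg mean: 0.75 × 0.994 + 0.25 × 0.744 = 0.932, which is 6.3% below Arm 1 alone.
- 300:150 ratio, Arm 1 against Arm 2: 2 × 0.994 / 1.24 = 1.60.
- 300:150 ratio, pooled 300 mg against Arm 2: 2 × 0.932 / 1.24 = 1.50.
- Dose-proportional steady-state value: 2.0.

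**Sensitivity to s (averages over Weeks 14 to 24)**

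| s | Arm 4 | Arm 2 | Pooled 300 mg vs Arm 1 | Pooled 300:150 ratio |
|---|---|---|---|---|
| 1 | 74% | 124% | −6.3% | 1.50 |
| 0.5 | 87% | 112% | −3.1% | 1.72 |
| 0.25 | 94% | 106% | −1.6% | 1.85 |
| 0.1 | 97% | 102% | −0.6% | 1.94 |
| 0.05 | 99% | 101% | −0.3% | 1.97 |

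**Sensitivity to half-life (s = 1, Week 14 to Week 24).** At 14 days, Arm 4 goes from 50% to 98% and Arm 2 from 150% to 102%. At 28 days, Arm 4 goes from 29% to 88% and Arm 2 from 161% to 111%.

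**The case against.** The strongest reply has four parts.

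First, the size rests on an unknown. Protocol 4.3 describes rapid distribution from plasma to tissue. If most of the plasma AUC arises in that early phase, the shift in AUC(0-168) is around 1% or less, and Cmax and AUC(0-24) may hardly move. This stands. A reader might infer that the 150 mg and 300 mg exposures are distorted as a matter of fact. The documents support only that AUC(0-168) can be biased.

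Second, pooling is not the main cause. A reader might blame pooling for the whole move from 2.0 to 1.5. Of that 0.5, 0.4 is carry-over within Arm 2 and remains if Arm 4 is left out. Nor does pooling of arms raise the 150 mg mean: by design only Arm 2 takes 150 mg in these weeks, and the documents give no number for participants resumed at 150 mg. Splitting by arm alone would therefore leave most of the effect in place.

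Third, other displays help. Sparse troughs are shown by arm and visit, individual intensive values are listed, and a population PK model is planned. All true. But troughs are not AUC, and the model is reported separately, so neither corrects the AUC(0-168) tables.

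Fourth, nothing is labelled steady state and no formal dose-proportionality analysis is planned. Also true, so misreading is a risk and not a planned inference. The plots are, however, to be compared between dose levels.

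A reader might also infer that regional PK comparisons are confounded by arm. With 13 profiles per region and 10% allocation to Arm 4, a region has no Arm 4 profile with probability 0.9^13 = 0.25, so the mix can differ by chance. The resulting difference depends on the same unknown share, so confounding of any particular size cannot be asserted.

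**Conclusion.** The concern holds as a presentation point on a descriptive secondary summary. The dose-level grouping combines histories that the stated half-life implies are not equivalent for much of Weeks 14 to 24, and AUC(0-168) can be biased as a result.

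At the upper bound (21-day half-life, one compartment, even spread of visits, 3:3:3:1 mix), Arm 4 averages 74% and Arm 2 124% of own-dose steady state. Pooling Arm 4 with Arm 1 lowers the 300 mg mean by about 6%. The 300:150 ratio reads about 1.6 from Arm 2 carry-over and about 1.5 after pooling. Even at this bound the departure fades, to 94% and 106% by Week 24.

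The lower end is close to zero, and the documents do not say where in the range the drug lies. The case for change rests on the low cost of a display that does not depend on that unknown, and not on a demonstrated error.

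**What to change.** In SAP 4.3.3.4, replace dose level with randomised arm (1, 2, 4) for the intensive GSK3228836 summaries, listings and plots, and:

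- Show weeks since first GSK3228836 dose for Arm 4 and weeks since step-down for Arm 2. This is the part that addresses the Arm 2 carry-over.
- Do not pool Arm 4 with Arm 1.
- Flag participants whose dosing was held and resumed, and show them separately.
- Add a footnote that Arm 2 and early Arm 4 values are not steady-state values and should not be used to compare 150 mg with 300 mg exposure.

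The cost is SAP wording, one grouping variable, one derived time variable and a footnote. No new data are needed. The downside is smaller groups: about 4 Arm 4 profiles are expected overall (3.9 / 3 = 1.3 per region), so for Arm 4 the listing and individual plots will be more informative than summary statistics.

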4.4. End of Study Definition

A participant is considered to have completed the study if he/she has completed all phases of the study including the last visit.

The end of the study is defined as the date of the last visit of the last participant in the study.

5. STUDY POPULATION

Prospective approval of protocol deviations to recruitment and enrollment criteria, also known as protocol waivers or exemptions, is not permitted.

5.1. Inclusion Criteria

AGE

1. At least 18 years of age at the time of signing the informed consent [if country/site age requirements for consent differ, the more stringent (e.g., higher age) restriction will be required for that country/site].

TYPE OF PARTICIPANT AND DISEASE CHARACTERISTICS

- 2. Participants who have documented chronic HBV infection ≥6 months prior to screening AND
 - a. Not currently on nucleos(t)ide analogue therapy population defined as participants who never received HBV treatment (treatment naïve) OR must have ended nucleos(t)ide therapy at least 6 months prior to the

screening visit

- b. OR Currently receiving stable nucleos(t)ide analogue therapy population defined as no changes to their nucleos(t)ide regimen from at least 6 months prior to screening and with no planned changes to the stable regimen over the duration of the study
- 3. Plasma or serum HBsAg concentration >100 IU/mL
- 4. Plasma or serum HBV DNA concentration
 - a. Participants not currently on nucleos(t)ide analogue therapy, plasma or serum HBV DNA >2000 IU/mL
 - Participants who are receiving stable nucleos(t)ide analogue therapy must be adequately suppressed, defined as plasma or serum HBV DNA <90 IU/mL
- 5. Alanine Transaminase (ALT)
 - a. ALT for treatment naïve participants and for participants who are not currently receiving treatment
 - i. ALT <3 X ULN will be included initially
 - If agreed by the IDMC after review of safety data, the ALT inclusion criteria may be expanded to include participants with ALT <5 X ULN
 - b. ALT ≤2 X ULN for participants who are receiving stable nucleos(t)ide analogue therapy

SEX

- 6. Male and/or Female
 - a. A male participant is eligible to participate if they agree to the following during the intervention period and for at least 90 days after the last dose of study treatment
 - i. Refrain from donating sperm
 - ii. AND be abstinent from heterosexual intercourse as their preferred and usual lifestyle (abstinent on a long term and persistent basis) and agree to remain abstinent OR Must agree to use contraception/barrier as detailed below
 - 1. Agree to use a male condom [and should also be advised of the benefit for a female partner to use a highly effective method of contraception as a condom may break or leak] when having sexual intercourse with a woman of childbearing potential who is not currently pregnant
 - b. A female participant is eligible to participate:

- i. If she is not pregnant or breastfeeding
- ii. AND at least one of the following conditions applies:
 - 1. Is not a woman of childbearing potential (WOCBP)
 - 2. OR is a WOCBP and using a contraceptive method that is highly effective (with a failure rate of <1% per year), preferably with low user dependency during the intervention period and for at least 90 days after the last dose of study treatment

iii. A WOCBP must have both

- 1. A confirmed menstrual period prior to the first dose of study intervention [additional evaluation (e.g., amenorrhea in athletes, birth control) should also be considered]
- 2. AND a negative highly sensitive pregnancy test [urine or serum] within 24 hours before the first dose of study treatment

Contraceptive use by men or women should be consistent with local regulations regarding the methods of contraception for those participating in clinical studies.

Additional requirements for pregnancy testing during and after study intervention are located in Appendix 2.

The investigator is responsible for review of medical history, menstrual history, and recent sexual activity to decrease the risk for inclusion of a woman with an early undetected pregnancy

INFORMED CONSENT

7. Capable of giving signed informed consent which includes compliance with the requirements and restrictions listed in the informed consent form (ICF) and in this protocol.

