10.4. Appendix 4: Contraceptive Guidance and Collection of Pregnancy Information

10.4.1. Definitions:

Woman of Childbearing Potential (WOCBP)

A woman is considered fertile following menarche and until becoming post-menopausal unless permanently sterile (see below).

If fertility is unclear (e.g., amenorrhea in adolescents or athletes) and a menstrual cycle cannot be confirmed before first dose of study intervention, additional evaluation should be considered.

Women in the following categories are not considered WOCBP

- Premenarchal
- Premenopausal female with 1 of the following:
 - Documented hysterectomy
 - Documented bilateral salpingectomy
 - Documented bilateral oophorectomy

For individuals with permanent infertility due to an alternate medical cause other than the above, (e.g., Mullerian agenesis, androgen insensitivity), investigator discretion should be applied to determining study entry.

Note: Documentation can come from the site personnel's: review of the participant's medical records, medical examination, or medical history interview.

- Postmenopausal female
 - A postmenopausal state is defined as no menses for 12 months without an alternative medical cause.
 - A high follicle stimulating hormone (FSH) level in the postmenopausal range may be used to confirm a postmenopausal state in women not using hormonal contraception or hormonal replacement therapy (HRT). However, in the absence of 12 months of amenorrhea, confirmation with more than one FSH measurement is required.
 - Females on HRT and whose menopausal status is in doubt will be required to use one of the non-estrogen hormonal highly effective contraception methods if they wish to continue their HRT during the study. Otherwise, they must discontinue HRT to allow confirmation of postmenopausal status before study enrollment.

10.4.2. Contraception Guidance:

CONTRACEPTIVES^a ALLOWED DURING THE STUDY INCLUDE:

- Highly Effective Methods^b That Have Low User Dependency Failure rate of <1% per year when used consistently and correctly.
 - Implantable progestogen-only hormone contraception associated with inhibition of ovulation^b
 - Intrauterine device (IUD)
 - Intrauterine hormone-releasing system (IUS) b
 - Bilateral tubal occlusion
 - Vasectomized partner

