Note: Vasectomized partner is a highly effective contraceptive method provided that the partner is the sole sexual partner of the woman of childbearing potential and the absence of sperm has been confirmed. If not, an additional highly effective method of contraception should be used. Spermatogenesis cycle is approximately 90 days.

- Highly Effective Methods^b That Are User Dependent Failure rate of <1% per year when used consistently and correctly.
- Combined (estrogen- and progestogen-containing) hormonal contraception associated with inhibition of ovulation^c
- oral
- intravaginal
- transdermal
- injectable
- Progestogen-only hormone contraception associated with inhibition of ovulation^c
- oral
- injectable
- Sexual abstinence
- Note: Sexual abstinence is considered a highly effective method only if defined as
 refraining from heterosexual intercourse during the entire period of risk associated with
 the study intervention. The reliability of sexual abstinence needs to be evaluated in
 relation to the duration of the study and the preferred and usual lifestyle of the
 participant.

ACCEPTABLE METHODS^d

- Progestogen-only oral hormonal contraception where inhibition of ovulation is not the primary mode of action
- Male or female condom with or without spermicide^e
- Cervical cap, diaphragm, or sponge with spermicide
- A combination of male condom with either cervical cap, diaphragm, or sponge with

spermicide (double-barrier methods)c

- a. Contraceptive use by men or women should be consistent with local regulations regarding the use of contraceptive methods for those participating in clinical studies.
- b. Failure rate of <1% per year when used consistently and correctly. Typical use failure rates differ from those when used consistently and correctly.
- c. If locally required, in accordance with Clinical Trial Facilitation Group (CTFG) guidelines, acceptable contraceptive methods are limited to those which inhibit ovulation as the primary mode of action.
- d. Considered effective, but not highly effective failure rate of ≥1% per year. Periodic abstinence (calendar, sympto-thermal, post-ovulation methods), withdrawal (coitus interruptus), spermicides only, and lactational amenorrhoea method (LAM) are not acceptable methods of contraception.
- Male condom and female condom should not be used together (due to risk of failure with friction).

10.4.3. Collection of Pregnancy Information:

Female Participants who become pregnant

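### Appendix 4 lists as allowed a group of contraceptive methods that inclusion criterion 6b rules out for women of childbearing potential

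*Protocol*

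**What the plan says.** Protocol Section 5.1, criterion 6b, makes a woman eligible if she is not of childbearing potential, or if she "is a WOCBP and using a contraceptive method that is highly effective (with a failure rate of <1% per year". The criterion continues "preferably with low user dependency during the intervention period and for at least 90 days after the last dose of study treatment". It names no method and does not refer to Appendix 4. The only onward reference for women in Section 5.1 is to Appendix 2, for pregnancy testing.

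Appendix 4, Section 10.4.2, has one heading, contraceptives "ALLOWED DURING THE STUDY INCLUDE", over three groups. Two are labelled highly effective, with failure below 1% per year: one with low user dependency, one user dependent. The third is labelled acceptable methods. It contains "Progestogen-only oral hormonal contraception where inhibition of ovulation is not the primary mode of action", the male or female condom, "Cervical cap, diaphragm, or sponge with spermicide", and double-barrier combinations.

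Three footnotes bear on this:

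- Footnote d rates the third group "Considered effective, but not highly effective failure rate of ≥1% per year".
- Footnote c narrows the choice only conditionally: "If locally required, in accordance with Clinical Trial Facilitation Group (CTFG) guidelines, acceptable contraceptive methods are limited to those which inhibit ovulation".
- Footnote b, attached to the highly effective groups, adds "Typical use failure rates differ from those when used consistently and correctly".

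**The concern.** The criterion and the only list of methods give different answers to the question a site will ask: which methods may a WOCBP use in this trial? Criterion 6b sets the bar below 1% failure per year. The appendix shows as allowed a group it rates at 1% or more.

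A site that settles contraception from the appendix could randomise a woman whom 6b excludes, or let a participant change to such a method during treatment. Section 5 does not permit waivers of enrolment criteria, so enrolling her would be an eligibility deviation that the protocol's own text invited. It would also carry an avoidable risk of pregnancy during exposure to an investigational antisense drug.

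The scheduled pregnancy tests detect a pregnancy; they do not prevent exposure. Section 10.4.3 has a participant who becomes pregnant stop treatment or leave the study. Because Section 4.3 gives a half-life of about three weeks, stopping does not end exposure at once.

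**Working it through.** No design figure has to be reproduced. The main check is a comparison of texts.

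| Question | Criterion 6b (Section 5.1) | Appendix 4 (Section 10.4.2), third group |
|---|---|---|
| Failure rate per year | below 1% | 1% or more (footnote d) |
| Class | highly effective | not highly effective (footnote d) |
| Status | required for entry | under the heading of allowed contraceptives |
| Stated link to the other text | none on methods | none to 6b |

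**Step 1: do the thresholds overlap?** No. A method failing in 1% or more of users per year cannot satisfy a requirement of less than 1%. Every method in the third group therefore fails 6b.

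**Step 2: could the group be meant for male participants?** No. It includes a progestogen-only pill, the female condom, cap, diaphragm and sponge. The men's requirement is set separately in criterion 6a, which asks for a male condom.

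**Step 3: does another sentence remove the conflict?** Footnote c applies only where local rules require it. Footnote d goes on to name methods that are not acceptable (periodic abstinence, withdrawal, spermicide alone, lactational amenorrhoea). That draws the line of acceptability below the third group, not above it.

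**Step 4: context on exposure.** These figures describe test spacing and drug persistence. They do not size the conflict.

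- Tests fall on Days 1, 29, 57, 85, 113 and 141, then off-treatment Day 1, planned for Day 169 (Section 1.3, Tables 2 to 4).
- Dosing visits from the Day 1 test up to the Day 29 test: Days 1, 4, 8, 11, 15 and 22, which is 6.
- Each of the five later intervals contains 4, for example Days 29, 36, 43 and 50. Total: 6 + 5 × 4 = 26, matching 24 weekly plus 2 loading visits.
- Not all are active doses. Arms 1 and 2 receive active drug at all 26. Arm 3 has 12 placebo visits (Days 85 to 162), leaving 14 active. Arm 4 has 14 placebo visits (Days 1 to 78), leaving 12 active.
- For a woman who completes dosing, 6b applies until at least Day 162 + 90 = Day 252.
- With a 21-day half-life and simple exponential decline (an assumption), the fraction of drug remaining 28 days after the last dose is 0.5^(28/21) = 0.397, about 40%.

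**The case against.** The strongest reply is that the rule is already clear. Appendix 4 sorts methods by the term that 6b uses, and footnote d denies the third group exactly the property that 6b demands. An investigator who reads both can tell which groups qualify. Appendix 4 also holds to the higher standard elsewhere: where a vasectomised partner does not meet its conditions, or where menopausal status is in doubt on hormone replacement, it asks for a highly effective method. Appendix 2 places eligibility requirements in Section 5, so 6b governs, and Section 8 requires every criterion to be confirmed at screening. Further safeguards are a review of menstrual and sexual history, a negative sensitive test within 24 hours before the first dose, and freedom to test more often. On this view, only a cross-reference is missing.

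Much of that stands. Criterion 6b does govern, a careful reader can infer the answer, and the exposure counts would be the same if every woman complied with 6b. What does not stand is that the inference is enough. The heading says allowed, footnote d's list of unacceptable methods stops short of this group, and no sentence says these methods fall short of 6b. The appendix adds explicit conditions to the vasectomised partner and to abstinence, yet adds none to the one group that fails eligibility. The other safeguards establish that a woman is not pregnant at the start, or find a pregnancy later; they do not settle which contraception she may use.

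**Conclusion.** The concern holds. The protocol states two incompatible positions on contraception for WOCBP: an eligibility rule of below 1% failure per year, and a list of allowed methods that includes a group rated at 1% or more. This is a conflict in the text as written.

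Its practical size cannot be estimated from the documents. They give neither the number of WOCBP nor the methods they use, and footnote d gives only a lower bound on the failure rate. No pregnancy rate is claimed, and there is no evidence that any site has followed the list rather than the criterion. The exposure figures show only why prevention matters more than detection here; the 40% figure rests on the stated half-life and on simple exponential decline.

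The estimands, endpoints and analyses are not affected. The point concerns participant safety and eligibility, and it should be corrected.

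**What to change.** In Appendix 4, Section 10.4.2, delete the acceptable-methods group for WOCBP, or state beside it that these methods alone do not satisfy criterion 6b and may be used only in addition to a highly effective method. Keep the male condom there only as the 6a requirement for male participants. In criterion 6b, add a reference to the corrected list. If the consent form repeats the list, change it to match.

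The drafting is small: one list and one cross-reference, with no new visits, tests or analyses. It is still a protocol amendment, and Section 10.1.1 requires ethics committee approval before such a change is implemented, in every participating country. Some candidates may have to change method or be unable to join, but only those whom 6b already excludes.
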